5.0 Benefits and risks of participants in the D-SOL Study

Results of the body composition, vitamin D status and dietary intake from the self-reported food diaries will be made available to the subjects upon request.

We do not anticipate identifying anything of concern via either the blood tests or bone scan, as we're not measuring any markers that would actually indicate any serious pathology is occurring. A letter informing that the participant is on the trial will be sent the participant's GP. A response from the GP will not be required unless the GP had concerns and no results will be sent to them afterwards. If the results are within healthy ranges the participants will not be contacted unless they specifically request for this information. If abnormal results came back for a participant, they will be offered support in approaching the GP, all the information regarding their test results, details on the intervention, etc, will be made available.

Due to the trial being food based, the risk of side-effects is minimal. However, gastrointestinal discomfort may occur following supplement consumption.

A blood sample must be taken at each trail visit, including screening, and due to the nature of the procedure, some light bruising may occur. Occasionally, fainting in some individuals can occur relating to venepuncture. TO help reduce the risk of this, participants will have their blood sample taken either whilst they are supine on a bed or reclined on a chair that has the capacity to be adapted quickly to allow the participant to lie supine safely if they do become unwell.

pQCT and DXA scans use a low level of radiation (much lower than standard X-ray examination) to which participants will be exposed. The amount of radiation absorbed from the scan is very small and similar to the radiation we receive from the environment.

Although health problems linked to vitamin D are very rare, there is some evidence that vitamin D supplementation can cause blood calcium levels to go higher than normal in some people who already have high blood calcium levels. Upon commencing the study, all participants will have their blood calcium levels checked to ensure that the vitamin D would be unlikely to cause any problems.

6. Ethics and regulatory approval

The trial will be conducted in compliance with the principles of the Declaration of Helsinki (2008), the principles of GCP and in accordance with The Medicines for Human Use (Clinical Trials) Regulations 2004 and Amended Regulations 2006.

This protocol and supporting documents will be submitted for review by the University of Surrey Ethics Committee and the Federal University of Goias, Brazil. Annual progress reports and a final report will be submitted to the ethics committees as defined in their respective regulations.

7.0 Study Evaluation and Statistical Analysis

Statistical analysis will be undertaken with support from the University of Surrey statistical department. Data will be checked for normality using appropriate testing. Appropriate parametric/non-parametric analysis will be applied.

The database will be stored and analysed using SPSS ® version 13.0.

The descriptive analysis, including mean ± standard deviation, median and lower limit and higher will be held for all quantitative variables Data will be checked for normality using appropriate testing. Appropriate parametric/non-parametric analysis will be applied. Student t test or Mann-Whitney test, depending on the distribution of data, will be applied to evaluate differences between supplemented and placebo. For analysis between Brazil and UK groups an ANOVA test will be undertaken. Linear correlation, Pearson or Spearman, will be calculated in accordance with the presence / absence of normal distribution, respectively, between vitamin D intake, sun exposure, skin pigmentation and vitamin D serum concentration. Multiple linear regression analysis will be performed to determine the variants that influence blood concentrations of vitamin D. In order to determine whether supplemental response differs between genotypes, these will be separated into wild homozygotes, heterozygotes and homozygotes for the variant. In this approach, the results will be evaluated with the test ANOVA or Kruskal-Wallis, in cases of variables with normal distribution or not, respectively. To describe the relationship between food intake aspects and features biochemical independent of energy intake, intake values of nutrients of interest will be adjusted to energy in accordance with the method. Significance considered as standard will be 5%.

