2.0 Objectives & Design

2.1 Primary Objectives: To examine the response (in vitamin D status) to vitamin D supplementation and sunlight exposure, and its influencing factors within and between Brazilian female adults living in the UK and Brazilian female adults living in Brazil.

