2.2 Secondary Objectives

- (i) Analyze the difference regarding time and intensity of sun exposure between Brazilian women living in Brazil and Brazilian women living in the UK.
- (ii) Determine the prevalence of inadequate dietary Vitamin D intake in these women.
- (iii) Determine the prevalence of insufficient/deficient levels of vitamin D in these women.
- (iv) To elucidate the association between Vitamin D status and markers of calcium of calcium metabolism.
- (v) Examine the influence of latitude on vitamin D optimal levels.
- (vi) Analyze the influence of skin pigmentation on vitamin D optimal levels.
- (vii) Analyze if response to Vitamin D supplementation is dependent on initial vitamin D levels.
- (viii) Investigate the genetic and enzymatic mechanisms underlying the adolescents' response to vitamin D supplementation via genotyping for polymorphisms related to vitamin D metabolism and comparing the high and low responders to supplementation (Genetic Sub-Study).

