2.3 Hypothesis

The study hypothesis that, during winter, vitamin D supplementation is required to obtain Vitamin D optimal levels in Brazilian women residing in the UK as well as Brazilian women residing in Brazil and that this response is dependent on the initial levels, being also influenced by sunlight exposure, skin pigmentation and polymorphisms of the vitamin D receptor gene.

H1: Dietary intakes of vitamin D are too low and sunlight exposure is insufficient for optimal vitamin D status in Brazilians living in the UK and Brazilians living in Brazil.

H2: The response of subjects to vitamin D supplementation is dependent on baseline 25OHD levels.

H3: Response to supplementation is influenced by sun light exposure.

H4: Skin pigmentation is an influential factor on vitamin D optimal levels.

H5: There will be strong genetic influences on 25OHD changes in response to vitamin D supplementation; these will be similar in both groups.

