3.0 Experimental Design

Two controlled, randomized, double-blind clinical trials will be developed and undertaken (one in Brazil and the other in the UK) with an intervention period of 12 weeks.

A questionnaire to screen for the relevant inclusion and exclusion criteria (see section A) will be administered in order to select 80 Brazilian female subjects, aged 20 to 59 years, in each of the two countries. The women selected will be randomly divided into two groups: Placebo Group and Supplemented Group, the latter will receive 600UI UI of vitamin D.

The first clinical trial will run in the UK from October 2016 to March 2017 (autumn-winter) and then the second will run in Brazil from April 2017 to September 2017 (autumn-winter). After the analysis of the effect of vitamin D supplementation compared to placebo, the results obtained in the supplemented group will also be analysed according to the genotypes for SNPs in the VDR gene.

We have chosen 12 weeks (3 months) as the supplementation period as we consider this to be ample time for 25OHD levels to rise (half-life of 25OHD is 3 weeks) and this has been demonstrated to be an effective timeframe for supplementation of vitamin D in previous studies.

We have chosen 600IU to enable the study to be relevant to the new IOM US recommendations for vitamin D, which are currently the reference document used in Brazil, even though the Brazilian nutritional table remains with the daily intake recommendation of 200 IU, which was the IOM recommendation in 1997. Compliance will be checked by compliance interviews during the trial and by empty packaging count.

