3.1 Sample Size and randomisation

A total of 80 subjects (at 90% power) are required for recruitment into the 600 IU vitamin D group vs placebo group for the RCT to be conducted in the UK and a total of 80 subjects (at 90% power) are required for recruitment into the 600 IU vitamin D group vs. placebo group for the RCT to be conducted in Brazil. This will enable us to detect a 0.6 SD size effect at 90% power in serum 25OHD levels between placebo and 600 IU in UK-dwelling Brazilian populations and Brazilians living in Brazil. These study numbers of 40 subjects for the vitamin D group and n 40 for the placebo group includes a 20% drop-out rate factored in.

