4.0 Trial Procedures

4.1 Trial visit activities

During this study the subjects will be asked to visit the Clinical Investigation Unit, FHMS, University of Surrey in the UK or the Research Clinic, Faculty of Nutrition, Federal University of Goias in Brazil, on two occasions, at the beginning of the study for baseline measurements and at the conclusion of the study.

We will examine four to eight fasted subjects per study morning.

Trial visits will last approximately 45-60 minutes each and take place in the morning (7am-11am). Participants will be offered refreshments at the end of their appointment.

Consenting and Screening

If participants wish to be screened for participation in the study, they will receive the Participant Information Sheet and then be checked against the study inclusion and exclusion criteria using the 'Screening Questionnaire' (Section A), to be administered by a member of the D-SOL Research Team by phone or self-reported by email.

Baseline visit

If eligible, participants will be invited for the baseline visit. At this visit, they will first be given time to discuss the Participant Information Sheet and any questions they may have regarding the study.

Informed consent will be discussed and participants will be asked to sign the consent form, and will be offered a copy to keep for themselves.

- Health and Lifestyle questionnaire to be administered by a member of the D-SOL Research Team.
- Anthropometrics and blood pressure measured, and fasted blood sample taken (serum 25OHD levels, 1,25-dihydroxy vitamin D, serum calcium, albumin, parathyroid hormone, C-terminal telopeptide (CTX) ≈25ml) with an additional ≈10 ml for genetic profiling and ≈15 for storage for future measurements of nutritional markers.
- pQCT scan of the non-dominant forearm for UK trial or DEXA scan for Brazil trial.
- Bioelectrical impedance analysis (BIA) for body composition.
- Provision of randomly assigned daily supplement (30 days' supply), food diaries and dosimeter (to be returned via SAE provided) and sunlight exposure diary to be returned at 12 week visit. Follow-up appointment details arranged (including interim visit telephone appointments and for re-supply of supplement).

Final visit

- Final adverse event/compliance interview completed with investigator.
- Daily outdoor exposure diary received from participant and check for consistency at visit.

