- Anthropometrics and blood pressure measured, and blood sample taken (serum 25OHD levels, 1,25-dihydroxy vitamin D, serum calcium, albumin, parathyroid hormone, C-terminal telopeptide (CTX) ≈25ml) with an additional ≈10 ml for genetic profiling and ≈15 for storage for future measurements of nutritional markers.
- Bioelectrical impedance analysis (BIA) for body composition.
- Dosimeter and 4-day food diary received from participant (sent to participant prior to appointment).

DNA profiling procedure - After 12 weeks RCT

• Selection of 48 participant samples encompassing the best and worst supplementation-responders in each group, subject to previous consent form participant. Vitamin D related genes will be genotyped in DNA isolated from the study blood samples, DNA will be extracted and vitamin D polymorphisms will be determined by University of Surrey's genetic labs.

A trained phlebotomist will take the blood samples required as part of the trial protocol. Medical cover will be available at all times.

Throughout the duration of the trial, the participants will be contacted via telephone on a fortnightly basis to discuss any issues with any adverse event and compliance and to maintain good communication with the participants. (Please see AE reporting form). In the case of a serious adverse event (SAE) this will be recorded (please see SAE reporting form) and we will report it to both the Sponsor (University of Surrey) and the Surrey Ethics Committee.

The final interview will be completed at the final study visit. Participants have also be asked to return any supplements that were missed to confirm compliance.

For University of Surrey participants: A peripheral quantitative computed tomography (pQCT) scan was performed on the participant's non-dominant forearm at the baseline visit, to measure volumetric bone mineral density at the 4% and 66% radial site. This will allow for separate measurements of trabecular vBMD and trabecular area (4% site) and cortical vBMD and cortical area (66% site), as well as strength strain index, a measure of bone strength. pQCT also measures bone geometry alongside bone density. Therefore the muscle cross sectional area can be determined, which is a measure of muscle force, to which bone strength is adapted to. One scan was performed at baseline only and effective exposure doses were between ~1.5-1.8uSv.

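### The supplemented-versus-placebo test names no outcome (12-week 25OHD or its change) and commits to no baseline adjustment; a pre-specified ANCOVA would settle both at almost no cost

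*Combined protocol and SAP*

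**What the plan says.** Section 7.0 gives one sentence on the comparison of arms: "Student t test or Mann-Whitney test, depending on the distribution of data, will be applied to evaluate differences between supplemented and placebo". It names neither variable nor time point.

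Other sections do not settle it:

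- Section 3.1 sizes each trial to "detect a 0.6 SD size effect at 90% power in serum 25OHD levels between placebo and 600 IU". This leans towards the 12-week value.
- Section 2.1 sets out "To examine the response (in vitamin D status) to vitamin D supplementation". This leans towards change.
- H5 in section 2.3 speaks outright of changes in 25OHD after supplementation.
- Section 3.0 mentions the analysis only in passing: "After the analysis of the effect of vitamin D supplementation compared to placebo".

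Both measurements will exist. Section 4.1 lists at the baseline visit "Anthropometrics and blood pressure measured, and fasted blood sample taken (serum 25OHD levels" and at the final visit "Anthropometrics and blood pressure measured, and blood sample taken (serum 25OHD levels".

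The protocol expects the starting level to matter. Secondary objective (vii) is to "Analyze if response to Vitamin D supplementation is dependent on initial vitamin D levels", and H2 reads "The response of subjects to vitamin D supplementation is dependent on baseline 25OHD levels". The multiple linear regression in section 7.0 looks for what influences vitamin D concentrations and names neither arm nor baseline 25OHD.

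**The concern.** One sentence covers two different tests, one on the 12-week value and one on the change. They estimate the same mean difference under randomisation, but their precision depends on how strongly baseline and final 25OHD are correlated. At a correlation of 0.7 or more their power differs by 20 points or more; at 0.5 it does not differ at all. Since section 3.1 does not say which SD the 0.6 refers to, the planned effect is not fully defined either.

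Adjusting for baseline by regression uses the same two measurements and, over a wide range of correlations, is more precise than either t-test. The point concerns only the within-country comparison of supplemented with placebo, not the Brazil-UK ANOVA.

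**Working it through.** **Inputs.** From section 3.1: 40 per arm per country including 20% drop-out, so 40 × 0.8 = 32 completers per arm; effect 0.6 SD; stated power 90%. From section 7.0: significance level 5%. Assumed: two-sided test, normal data, equal SDs at both visits, and a baseline-to-final correlation r of 0.3 to 0.8, because the documents give none.

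**The plan's own figure.** The standard error of a difference in final values is √(2/32) = 0.25 SD, so the noncentrality is 0.6/0.25 = 2.40 on 62 df and power is 65.6%. With all 40 per arm it is 75.5%. The stated 90% is not reproduced; 60 completers per arm would be needed. That shortfall is a separate issue. Here 65.6% serves only as the starting point.

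**Formulas, with 0.6 SD on the final value.**

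- Final-value t-test: SD 1, 62 df.
- Change t-test: SD √(2(1−r)), 62 df. At r = 0.7: √0.6 = 0.775; 2.40/0.775 = 3.10; power 86.2%.
- ANCOVA: residual SD √(1−r²), variance multiplied by 1 + 1/60 for estimating the slope, 61 df. At r = 0.5: 0.866 × 1.0083 = 0.873; 2.40/0.873 = 2.75; power 77.2%.

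| r | Final-value t | Change t | ANCOVA | Gain over better t-test |
|---|---|---|---|---|
| 0.3 | 65.6% | 51.5% | 69.0% | 3 points |
| 0.5 | 65.6% | 65.6% | 77.2% | 12 points |
| 0.6 | 65.6% | 75.2% | 83.4% | 8 points |
| 0.7 | 65.6% | 86.2% | 90.7% | 4 points |
| 0.8 | 65.6% | 96.2% | 97.4% | 1 point |

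The gain peaks near r = 0.5, where the two t-tests tie.

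**If 0.6 SD is instead the SD of change**, at r = 0.3, 0.5, 0.6, 0.7, 0.8: final-value t 80, 66, 56, 45, 32%; change t 66% throughout; ANCOVA 83, 77, 75, 72, 69%. ANCOVA is again ahead of both, by about 3 to 12 points over the better one.

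**Half-width of the 95% CI**, in SDs of the final value, at r = 0.3, 0.5, 0.7: final value 0.50 throughout; change 0.59, 0.50, 0.39; ANCOVA 0.48, 0.44, 0.36.

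**Where ANCOVA loses to a t-test.** It breaks even with the final-value test at r of about 0.13; at r = 0 it has 64.9% against 65.6%. If the slope on baseline is 1 (baseline SD 0.7 of final SD, r = 0.7), it has 90.7% against 91.1% for change. Both losses are under 1 point.

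**Skewed data.** Section 7.0 plans the Mann-Whitney test for non-normal data, so it must be compared too. Simulation with lognormal values (log SD 0.5), 32 per arm, r = 0.3, 0.5, 0.7:

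- Additive shift of 0.6 SD, r set on the log scale: the better Mann-Whitney test (final value or change) has 81, 82, 91% against 70, 76, 89% for original-scale ANCOVA, a loss of 11, 6 and 2 points.
- Additive shift, r set on the original scale: Mann-Whitney 81, 82, 94%; original-scale ANCOVA 71, 79, 91%; log-scale ANCOVA 88, 94, 99%.
- Multiplicative effect: Mann-Whitney 57, 61, 82%; original-scale ANCOVA 58, 66, 82%; log-scale ANCOVA 64, 73, 88%.

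**Standard errors.** In simulations under no effect (normal data, unequal slopes and lognormal data), ordinary standard errors kept the type I error of ANCOVA at 4.8 to 5.1%.

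**The case against.** The strongest objection is that the planned test is already sound and that adjustment is not always better. Both parts stand. Randomisation makes the unadjusted comparison valid. With strongly skewed data and an additive effect, the planned Mann-Whitney test beats ANCOVA on the original scale. So adjustment cannot be called free in every case, and the scale has to be chosen deliberately. Log-scale ANCOVA did better than every planned test in the skewed cases simulated, but it estimates a ratio of geometric means, and the Mann-Whitney test targets a different quantity again.

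It may also be said that the planned multiple regression could include arm and baseline. It could, but section 7.0 names neither and gives it another purpose, so nothing commits the analysis to an adjusted arm comparison.

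Four stronger readings are tempting and not supported:

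- *That the plan ignores baseline 25OHD.* The unnamed outcome may be change, as H5 suggests, and change uses baseline by subtraction. Only the lack of a committed adjustment can be shown.
- *That the gain is 3 to 32 points.* That follows only if the final value is what is tested and the 0.6 SD refers to it. Section 3.1 leans that way, but section 2.1 and H5 lean the other.
- *That the outcome will be chosen after seeing results.* Section 7.0 makes only the choice between parametric and non-parametric tests depend on the data. It is silent on when the variable is fixed.
- *That adjustment rescues the stated 90% power.* On the final-value reading it does so only at r of about 0.69 or more.

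**Conclusion.** The point holds as a cheap improvement, not as an error that invalidates the trial. The tested variable is undefined, and a baseline-adjusted comparison, possible with data already being collected, is not committed to. The gain over the better t-test is about 1 to 12 points of power, for r between 0.3 and 0.8. That range rests on 32 completers per arm, a two-sided 5% level, normal data and equal SDs. It does not extend to the Mann-Whitney test on skewed data, where the choice of scale decides whether adjustment gains or loses. Every value of r is an assumption; the absence of an outcome definition in section 7.0 depends on none of them.

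**What to change.** In section 7.0, replace the sentence on the arm comparison with text to this effect: in each country the primary comparison is an ANCOVA (linear regression) of 12-week serum 25OHD on randomised arm with baseline 25OHD as covariate; the adjusted difference is reported with its 95% CI; the t or Mann-Whitney test on 12-week 25OHD is a sensitivity analysis.

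Fix the scale in a dated text before unblinding: original, or log for both measurements if 25OHD is expected to be skewed, in which case the effect is reported as a ratio of geometric means. Allow no switch based on unblinded results. Ordinary standard errors suffice.

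In section 3.1, state whether 0.6 SD refers to the final value or to change. H2 needs its own arm-by-baseline term in a secondary model, since the primary ANCOVA does not test it.

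Cost: wording in two sections, no new samples or visits, and one degree of freedom per country. Linear regression is already a planned method. Against the t-tests the downside is under 1 point of power if r is below about 0.13 or the slope is near 1. Against the Mann-Whitney test it is about 2 to 11 points if the original scale is kept for strongly skewed data with an additive effect.

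### A normality check on the trial data picks the arm-comparison test, so the primary comparison may be only a rank-test p-value, and UK and Brazil may by chance get different tests

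*Combined protocol and SAP*

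**What the plan says.** The primary objective in section 2.1 is the response in vitamin D status to supplementation and sunlight, and "its influencing factors within and between Brazilian female adults living in the UK and Brazilian female adults living in Brazil". Section 3.0 sets up two randomised trials, the UK one first and the Brazil one after it. Section 3.1 sizes each separately, for a 0.6 SD difference in serum 25OHD between placebo and 600 IU.

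Section 7.0 gives the analysis. First, "Data will be checked for normality using appropriate testing". Then "Student t test or Mann-Whitney test, depending on the distribution of data, will be applied to evaluate differences between supplemented and placebo". Genotype comparisons follow the same pattern: "the results will be evaluated with the test ANOVA or Kruskal-Wallis, in cases of variables with normal distribution or not, respectively". Correlations switch between Pearson and Spearman on the same basis.

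Three other commitments in section 7.0 bear on the point:

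- The between-country method: "For analysis between Brazil and UK groups an ANOVA test will be undertaken".
- The descriptive summary: "The descriptive analysis, including mean ± standard deviation, median and lower limit and higher will be held for all quantitative variables".
- A multiple linear regression for blood vitamin D.

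Section 7.0 does not name the normality test or its threshold. It does not say whether final values, changes or residuals are checked, or whether the check is per arm, per trial or pooled. It names no treatment-effect estimate and no confidence interval.

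**The concern.** Letting the observed distribution choose the test leaves the main result unfixed until the data are in. With two separately sized trials run one after the other, a check within each trial is the natural reading. The verdict of a normality test at this sample size is partly chance, so the two countries could be sent to different tests even if 25OHD behaved identically in both.

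The form of the result is also at stake. The objective and the sample size are both about the size of a response, the latter on a mean-difference scale. A Mann-Whitney test, as the plan specifies it, yields a p-value. It does not by itself give a difference in 25OHD units, and it carries no terms for country, baseline, sun exposure or skin pigmentation, which hypotheses H2 to H4 treat as influential.

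**Working it through.** **Inputs from the documents.** Section 3.1 gives 40 per arm in each trial with 20% drop-out included, so completers per arm are 40 × 0.80 = 32. The effect of interest is 0.6 SD and the significance level is 5% (section 7.0; two-sided assumed).

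**The plan's own figure.** The usual two-arm formula gives n = 2 × ((1.960 + 1.282)/0.6)² ≈ 58.4, so 59 per arm, and 59/0.80 = 73.75, so 74 per arm (148 per trial). The stated 80 per trial is not reproduced. That is a separate matter, and nothing below depends on it. The figure of 32 is used only as the planned number of completers.

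**Assumptions, because the documents give no SD or distribution for 25OHD.** Shapiro-Wilk at 5%, run within each trial, in one of two ways:

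- per arm: Mann-Whitney is used if either arm rejects normality;
- residuals: one test on the arm-centred values of both arms together.

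Both countries are drawn from the same distribution, with 4,000 simulated trials per row. For a log-normal, CV = √(exp(σ²) − 1), so σ = 0.2, 0.3, 0.4 and 0.5 correspond to CVs of about 20%, 31%, 42% and 53%.

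**Step 1: chance of different tests.** If p is the chance that one trial is sent to Mann-Whitney, two independent trials differ with probability 2p(1 − p). For normal data with the per-arm check, 2 × 0.098 × 0.902 = 0.177.

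| Distribution, 32 per arm | p, per arm | Different tests | p, residuals | Different tests |
|---|---|---|---|---|
| Normal | 9.8% | 18% | 5.0% | 9% |
| Gamma, shape 20 | 23.4% | 36% | 21.2% | 33% |
| Gamma, shape 10 | 39.6% | 48% | 41.1% | 48% |
| Gamma, shape 5 | 62.6% | 47% | 68.1% | 43% |
| Log-normal, σ 0.2 | 36.5% | 46% | 36.2% | 46% |
| Log-normal, σ 0.3 | 62.0% | 47% | 65.4% | 45% |
| Log-normal, σ 0.4 | 82.3% | 29% | 87.3% | 22% |
| Log-normal, σ 0.5 | 94.5% | 10% | 96.6% | 7% |

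The ceiling is 50%, reached at p = 0.5. Discordance falls again under strong skew because both trials then nearly always go to Mann-Whitney. A single check on both countries' data together gives 0% by construction.

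If response means change from baseline, skew is reduced. With an assumed baseline-to-final correlation of 0.7 (3,000 runs), discordance is 18–27% at CV 20%, 33–38% at CV 30% and about 49–50% at CV 45%.

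**Step 2: does the choice of test change the conclusion?** With a true shift of 0.6 SD and 32 per arm, power and disagreement at 5% on the same data were:

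| Log-normal σ | t test | Mann-Whitney | Disagree |
|---|---|---|---|
| 0.2 | 65.9% | 66.8% | 8.0% |
| 0.3 | 64.3% | 69.5% | 9.6% |
| 0.4 | 66.0% | 75.3% | 12.8% |

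Normal data give about 7%, so the range is about 7–13%.

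**Step 3: false positives.** With no treatment effect, the two-stage rule (check, then the chosen test) rejected in 4.3–5.8% of simulated trials, close to the nominal 5%.

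**The case against.** The strongest reply is that the plan does not rest on the arm-comparison test alone. The between-country comparison is assigned an ANOVA, and it is the only group comparison in section 7.0 with no named rank alternative. Means and SDs will be reported for every quantitative variable, so a mean difference and its interval can be worked out in each country whichever test supplies the p-value. The regression works on means and can carry covariates. All of this stands. A reader might infer that a t test in one country and a Mann-Whitney in the other would leave the two results impossible to compare. The documents do not support that.

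It is also fair that a Mann-Whitney test can be accompanied by a Hodges-Lehmann shift in 25OHD units. The plan simply does not name one. Nor does it mention a log or any other transformation, so the choice left open is between parametric and rank methods, not among several scales.

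Finally, the discordance figures depend on an assumed pre-test, distribution and unit of checking, and a pooled check removes discordance altogether. That stands too, and it is why the result is given as a range that includes zero.

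What the reply does not supply is a pre-specified treatment effect. The ANOVA's outcome and factors are unstated, no treatment-by-country term is mentioned, and the regression is described for blood concentrations rather than for the effect of supplementation.

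**Conclusion.** The point holds in a limited form. Section 7.0 lets an unnamed check on the trial data choose the primary arm-comparison test and the genotype test. If the check is run by trial, the two countries can be given different tests by chance: about 9–18% of the time with normal data and up to about 50% with skewed data, on the stated assumptions, and 0% under one pooled check.

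The consequence is a primary comparison that may amount to a rank-test p-value, with no common effect estimate fixed in advance and a 7–13% chance that the two candidate tests disagree under a 0.6 SD shift.

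Two stronger readings are tempting and should not be drawn. The first is that the rule inflates false positives: the simulated type I error is 4.3–5.8%. The second is that the analyst is free to pick the result: the rule itself is stated, and what is open is how the check is carried out. The trial remains analysable. This is an improvement the sponsor should make, not a flaw that invalidates the design.

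**What to change.** Before unblinding, amend section 7.0 to:

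- specify one linear model for 25OHD, on one scale chosen in advance (raw or log), and use it in both countries;
- report the treatment effect with a 95% interval in each country, and their difference through a treatment-by-country term;
- use the same scale for the genotype analyses;
- use normality checks only as model diagnostics, and keep Mann-Whitney and Kruskal-Wallis as sensitivity analyses.

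This needs no extra participants, visits or assays. It costs a wording change and a little more analysis work. The choice of scale has a price that should be accepted knowingly. On the log scale, effects are ratios that need back-transforming for readers, and the question in H2, whether response depends on baseline, is answered in relative terms. The raw scale stays closer to the mean-difference framing of section 3.1. Either is defensible if it is fixed beforehand.
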